8.2.6. Time to first CDA, CR, End of Consolidation Phase, and Relapse

Time to first CDA is defined as the following:

$$\text{Time to first CDA} = \text{Date of the first CDA confirmed} - \text{Date of first dose} + 1.$$

Time to first CR and End of Consolidation Phase are defined in the same way as Time to first CDA.

Time to first relapse after PRN1008 treatment completion or discontinuation is defined as the following:

$$\text{Time to first Relapse} = \text{Date of the first relapse after Week 13 visit confirmed} - \text{Date of last PRN1008 dose} + 1.$$

If the date of last PRN1008 dose is missing, the date of the Week 13 visit during treatment will be used. If patients did not complete the Week 13 visit they will be excluded from the relapse analysis.

The time to relapse analysis will be conducted in two subpopulations for each analysis population: 1) Patients with CDA at the Week 13 visit, 2) Patients with CR at the Week 13 visit.

Patients who have not achieved the above events by the date of study completion or discontinuation will be censored at the date of completion or discontinuation respectively.

Kaplan-Meier survival distribution plots for time to each event will be provided. Kaplan-Meier estimates of quartiles in days and its associated 80% and 95% CI will be calculated by using the LOGLOG transformation. Min and Max survival times in days as well as number of the patients and the probability of experiencing the event on or before specific date will be provided in a table.

The CDA status, CR status, End of Consolidation Phase status, and Relapse status by visit, by patient will be presented in a listing.

Duration of CR will be summarized and listed, and is defined by the last known CR date – first known CR date + 1. Each subject will only have one CR date as a result.

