Patients who have not achieved End of Consolidation Phase by the date of study completion or discontinuation will be censored at the date of completion or discontinuation.
Source Data: Table 14.2.3.3

<DIRECTORY PATH>PROGRAM NAME Executed: DDMMYYYY hh:mm

Prog NOTE: Please also add "all dose levels" in this plot.

[figure not shown]
Repeat for the following population

Figure 14.2.3.3.2
Kaplan Meier Plots for Time to First End of Consolidation Phase
mITT Population

Figure 14.2.3.3.3
Kaplan Meier Plots for Time to First End of Consolidation Phase
PP Population

Figure 14.2.3.4.1

Kaplan Meier Plots for Time to First Relapse after PRN1008 Treatment Completion or Discontinuation
ITT Population

Note: Patients are classified into different dose levels according to the maximum dose they received during the 12 week treatment period.
Relapse/flare: Appearance of ≥ 3 new lesions/month that do not heal spontaneously within 1 week, or by extension of established lesions, in a patient who has achieved disease control.
Only patients with confirmed CDA before treatment completion or discontinuation will be included into this analysis.
Time to first relapse = Date of first relapse confirmed - Date of last dose + 1.
Patients who have not achieved Relapse by the date of study completion or discontinuation will be censored at the date of completion or discontinuation.

Source Data: Table 14.2.3.4

<DIRECTORY PATH>PROGRAM NAME Executed: DDMMYYYY hh:mm

Prog NOTE: Please also add "all dose levels" in this plot.
Repeat for the following populations.

Figure 14.2.3.4.2

[figure not shown]
Kaplan Meier Plots for Time to First Relapse after PRN1008 Treatment Completion or Discontinuation
mITT Population

Figure 14.2.3.4.3

Kaplan Meier Plots for Time to First Relapse after PRN1008 Treatment Completion or Discontinuation
PP Population

Figure 14.3.3.2

Scatter Plots of Peak TBL vs Peak ALT for Identification of Drug Induced Liver Injury (DILI)
Safety Analysis Population

Note: Patients are classified into different dose levels according to the maximum dose they received during the 12 week treatment period.
TBL = total bilirubin, ALT = alanine aminotransferase or SGPT
The maximum measurement value observed during the 12 week treatment will be defined as the Peak value.

Source Data: Listing 16.2.6.2

<DIRECTORY PATH>PROGRAM NAME Executed: DDMMYYYY hh:mm

Listing 16.2.1.1
 Patient Disposition
 Screening Population

Maximum Dose Level: XXX mg

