Note: Sex: M=Male, F=Female; Race: W=White, BL=Black or African American, AS=Asian, AI=American Indian or Alaska Native, PI=Native Hawaiian or Other Pacific Islander, O=Other, FSNC=French Sites Only - Not Collected

Control of disease activity (CDA) is defined as the time at which new lesions cease to form and established lesions begin to heal.

Time to first CDA = Date of first CDA confirmed - Date of first dose + 1. Patients who did not achieve CDA by the date of study completion or discontinuation were censored at the date of completion or discontinuation respectively.

<DIRECTORY PATH>PROGRAM NAME Executed: DDMMYYYY hh:mm

Prog Note: Sort by Maximum Dose Level (400 mg, 500 mg, 600 mg, missing), Patient ID, Visit.

Listing 16.2.4.1.7
 Time to First Complete Response (CR)
 IIT Population

Maximum Dose Level: XXX mg

Patient ID	Age (yrs) / Sex / Race	Analysis Set	First Dose Date / Last Dose Date	Date of First CR or Censored Date	Time to First CR (Days)	Censored
XXXXXX	50/M/W	Safety/ Efficacy	DDMMYYYY/ DDMMYYYY	DDMMYYYY	xx	Yes
				DDMMYYYY	xx	Yes
				DDMMYYYY	xx	Yes
				DDMMYYYY	xx	No
			

Note: Sex: M=Male, F=Female; Race: W=White, BL=Black or African American, AS=Asian, AI=American Indian or Alaska Native, PI=Native Hawaiian or Other Pacific Islander, O=Other, FSNC=French Sites Only - Not Collected
 Complete response (CR) is defined as the absence of new or established lesions while the patient is receiving minimal or no non-PRN 1008 immunotherapy.
 Time to first CR = Date of first CR confirmed - Date of first dose + 1. Patients who did not achieve CR by the date of study completion or discontinuation were censored at the date of completion or discontinuation respectively.

<DIRECTORY PATH>PROGRAM NAME Executed: DDMMYYYY hh:mm

Prog Note: Sort by Maximum Dose Level (400 mg, 500 mg, 600 mg, missing), Patient ID, Visit.

Listing 16.2.4.1.8
 Time to First End of Consolidation Phase
 IIT Population

Maximum Dose Level: XXX mg

Patient ID	Age (yrs) / Sex / Race	Analysis Set	First Dose Date / Last Dose Date	Date of First End of Consolidation Phase or Censored Date	Time to First End of Consolidation Phase (Days)	Censored
XXXXXX	50/M/W	Safety/ Efficacy	DDMMYYYY/ DDMMYYYY	DDMMYYYY	xx	Yes
				DDMMYYYY	xx	Yes
				DDMMYYYY	xx	Yes
				DDMMYYYY	xx	No
			

Note: Sex: M=Male, F=Female; Race: W=White, BL=Black or African American, AS=Asian, AI=American Indian or Alaska Native, PI=Native Hawaiian or Other Pacific Islander, O=Other, FSNC=French Sites Only - Not Collected

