 End of consolidation phase: The time at which no new lesions have developed for minimum of 2 weeks, approximately 80% of lesions have healed, and when most clinicians start to taper steroids.
 Time to first end of consolidation phase = Date of first end of consolidation phase confirmed - Date of first dose + 1. Patients who did not achieve end of consolidation phase by the date of study completion or discontinuation were censored at the date of completion or discontinuation respectively.

<DIRECTORY PATH>PROGRAM NAME Executed: DDMMYYYY hh:mm

Prog Note: Sort by Maximum Dose Level (400 mg, 500 mg, 600 mg, missing), Patient ID, Visit.

Listing 16.2.4.1.9

Time to First Relapse after Week 13 Visit
 ITT Population

Maximum Dose Level: XXX mg

Patient ID	Age (yrs) / Sex / Race	Analysis Set	First Dose Date / Last Dose Date	Date of First Relapse After Week 13 or Censored Date	CDA at Week 13	CR at Week 13	Time to First Relapse From Week 13 (Days)	Censored
XXXXXX	50/M/W	Safety/ Efficacy	DDMMYYYY / DDMMYYYY	DDMMYYYY	Yes/No	Yes/No	xx	Yes
				DDMMYYYY	Yes/No	Yes/No	xx	Yes
				DDMMYYYY	Yes/No	Yes/No	xx	Yes
				DDMMYYYY	Yes/No	Yes/No	xx	No
							...	
							...	

Note: Sex: M=Male, F=Female; Race: W=White, BL=Black or African American, AS=Asian, AI=American Indian or Alaska Native, PI=Native Hawaiian or Other Pacific Islander, O=Other, FSNC=French Sites Only - Not Collected
 Relapse/flare: Appearance of >=3 new lesions/month that do not heal spontaneously within 1 week, or by extension of established lesions, in a patient who has achieved disease control. Only patients with confirmed CDA before treatment completion or discontinuation will be included into this listing.
 Time to first relapse = Date of first relapse confirmed after week 13 - Date of week 13 visit + 1.
 Patients who did not achieve relapse by the date of study completion or discontinuation were censored at the date of completion or discontinuation respectively.

<DIRECTORY PATH>PROGRAM NAME Executed: DDMMYYYY hh:mm

Prog Note: Sort by Maximum Dose Level (400 mg, 500 mg, 600 mg, missing), Patient ID, Visit.

Listing 16.2.4.1.10

Duration of Complete Response (CR) Status Among CR Subjects
 ITT Population

Maximum Dose Level: XXX mg

Patient ID	Age (yrs) / Sex / Race	Analysis Set	CR Start Date	Last Known CR Date	Last Follow up Date	Duration [1]
XXXXXX	50/M/W	Safety/ Efficacy	DDMMYYYY	DDMMYYYY	DDMMYYYY	Xx
XXXXXX	32/F/W	Safety/ Efficacy	DDMMYYYY	DDMMYYYY	DDMMYYYY	xx

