5.4.2.2 Time-to-Event

The following time-to-event analyses will be performed by dose level and overall for events occurred after date of first study drug dosing:

- a) Time to first CDA
- b) Time to first CR
- c) Time to first ECP
- d) Time to first relapse (after CDA has been achieved, as per the definition of relapse) after first dose of study drug
- e) Time to first increase in PDAI

For each event listed above, the number of days to the event will be calculated as:

(Date of first occurrence of event – Date of first study drug dosing of the dose level where the event is observed) + 1

The number of days to first occurrence of each event (a to d) will be summarized by descriptive statistics for each dose level and overall.

Patients who did not achieve the specific event are censored at the last day in a dose level or date of study completion/discontinuation.

Kaplan-Meier estimates of quartiles in days and their associated 80% and 95% CI will be calculated by using the LOGLOG transformation. Minimum and maximum survival times in days as well as number of the patients and the probability of experiencing the event on or before specific date will be provided in a table.

A sensitivity analysis using the Completer and PP populations will be provided.

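### Event-free patients are censored at the study completion or discontinuation date rather than at the last disease assessment, so cumulative incidence, including relapse, can be understated when patients leave unexamined

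*SAP*

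**What the plan says.** Part A SAP section 8.2.6 covers time to first CDA, CR, end of consolidation and relapse. Patients without the event "will be censored at the date of completion or discontinuation respectively". The estimator is Kaplan-Meier: "Kaplan-Meier survival distribution plots for time to each event will be provided".

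The Part A output shells repeat the rule:
- Listing 16.2.4.1.9 (relapse): "Patients who did not achieve relapse by the date of study completion or discontinuation were censored at the date of completion or discontinuation respectively".
- Listing 16.2.4.1.6 (CDA): "Patients who did not achieve CDA by the date of study completion or discontinuation were censored at the date of completion or discontinuation respectively".
- Figure 14.2.3.4.1 (relapse curve): "Patients who have not achieved Relapse by the date of study completion or discontinuation will be censored at the date of completion or discontinuation".

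For relapse, section 8.2.6 also limits who enters: "If patients did not complete the Week 13 visit they will be excluded from the relapse analysis".

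Part B SAP section 5.4.2.2 reads: "Patients who did not achieve the specific event are censored at the last day in a dose level or date of study completion/discontinuation". It does not say which date goes with which column. The natural reading is that the completion or discontinuation date applies to the Overall column, and this point is confined to that column.

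Disease scoring falls every four weeks after Week 5, and also at unscheduled visits (Part A SAP Appendix 15.1; Part B SAP Table 1). Neither schedule has an early-termination visit. Protocol section 16.4 asks for a final evaluation at withdrawal and for attempts to reach the participant by telephone, mail or a personal visit. It does not name the disease scores.

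**The concern.** Disease status is known only as far as the last assessment. A patient who stops attending may have a discontinuation date entered weeks later, for example after attempts at contact. Under the rule that patient stays in the risk set, counted as event-free, until that date. Loss to follow-up is a listed withdrawal reason in both SAPs, and I found no rule for dating it.

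The SAPs treat unknown status differently elsewhere. For the primary endpoint, unknown CDA status at Week 5 counts as non-response, which works against the drug. Duration of CR stops at the last known CR date. For relapse, unknown status becomes relapse-free time, which works for the drug. Relapse after stopping PRN1008 is a protocol secondary outcome (section 11.2). In Part A it is analysed only in patients with CDA, or with CR, at Week 13 of a study planned for 25, so a few late dates could move the curve.

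**Working it through.** **The plan's own figure.** The only design figure is an 80% CI of ±13% for a 50% response rate in 25 patients. It reproduces: 1.2816 × √(0.5 × 0.5 / 25) = 0.128. It gives a sense of scale but does not bear on censoring. Every relapse and dropout input below is an assumption.

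**Worked example.** Take 12 patients in CDA at Week 13. Relapses are recorded at days 29 (1 patient), 57 (2) and 85 (2) after last dose. Four patients complete, and three drop out after being last examined at day 29. Cumulative relapse at day 85 is one minus the product of the survival steps.

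| Censoring date of the three dropouts | Survival product | Relapse by day 85 |
|---|---|---|
| Last examination (day 29) | 11/12 × 6/8 × 4/6 = 0.458 | 54.2% |
| Discontinuation at day 50 | 11/12 × 6/8 × 4/6 = 0.458 | 54.2% |
| Discontinuation at days 60 to 80 | 11/12 × 9/11 × 4/6 = 0.500 | 50.0% |
| Discontinuation after day 85 | 11/12 × 9/11 × 7/9 = 0.583 | 41.7% |

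The day 50 row shows the condition. Nothing changes until the late date reaches another patient's recorded event time.

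**Simulation.** There were 12 or 20 patients, a median time to relapse of 60 or 120 days, dropout of 0, 10, 20 or 30%, and 1,500 data sets per setting. The table gives the mean 85-day relapse under the SAP rule minus that under last-examination censoring.

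| Setting | Difference (points) |
|---|---|
| No dropout | 0.0 |
| Relapse dated at visits, discontinuation before the next visit | 0.0 |
| Relapse dated between visits, discontinuation before the next visit | −0.6 to −2.5 |
| Discontinuation recorded 28 days late, relapse dated at visits | −1.1 to −5.0 |
| Discontinuation recorded 28 days late, relapse dated between visits | −1.6 to −7.1 |

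The largest gap came with 20 patients, a 60-day median and 30% dropout. The true value was 62.5%, the SAP rule gave 55.4% and last-examination censoring gave 62.5%. Across all settings, last-examination censoring stayed within about 1 point of the truth.

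**Extreme case.** Let m of 20 patients never be examined after Week 13 and be dated at the end of follow-up. Nobody is then censored early, and Kaplan-Meier reduces to the crude proportion. With an assumed median of 84 days, true 85-day relapse is 1 − 2^(−85/84) = 50.4%, and the rule gives 50.4% × (20 − m)/20. For m = 1, 2, 3 and 4 that is 47.9%, 45.4%, 42.8% and 40.3%, or shortfalls of about 2.5, 5.0, 7.6 and 10.1 points.

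**Direction.** Extra time at risk enlarges the denominators at later event times. This lowers cumulative incidence and lengthens quartiles for all the endpoints alike. Only the interpretation differs, because relapse is unfavourable and the other three events are favourable.

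**The case against.** The strongest reply is that the effect is conditional and may be nil. Completers are scored at their final visit, so for them the censoring date and the last assessment coincide. Part A relapse excludes anyone without a Week 13 visit. Protocol 16.4 asks for an exit evaluation. A late date would show in the patient listing. Part B adds sensitivity analyses in the Completer and per-protocol populations, which require a Week 29 assessment or visit. These are secondary endpoints in an open-label pilot. One lost patient of 20 costs 2.5 points even in the extreme case, against an 80% half-width of about 14 points (1.2816 × √(0.25/20) = 0.143).

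Most of this stands as a limit on size. A reader might infer that relapse is understated as a matter of course. The documents do not support that, because they give no dropout rate and no evidence of late dating. A reader might also take 2.5 to 10 points as an estimate. It restates an assumed extreme. Nor does the rule bias CDA, CR and consolidation upwards; it lowers those estimates too.

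The reply does not remove the point. An exit evaluation cannot be obtained from someone who stops attending. Part B's Completer and per-protocol analyses select on completion and leave the main mITT estimate as it is. Part A's per-protocol population needs only the Week 13 visit, so it does not screen out later losses. A dating artefact with one sign is a different matter from sampling error.

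**Conclusion.** The point holds as a conditional defect. Both SAPs let the risk set run past the last disease assessment. Where a patient leaves unexamined and is dated late enough, cumulative incidence is understated, to the drug's advantage for relapse and to its disadvantage for CDA, CR and end of consolidation. There is no effect for patients examined at completion or exit.

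The size rests wholly on assumed relapse rates, dropout and dating. It is 0 to about 7 points in the simulated settings, and about 10 points in the extreme case with 4 of 20 patients. The calculations concern relapse after stopping treatment in Part A. Part B counts relapse from dosing, so these figures do not carry over to it. The change is worth making because the rule is explicit and the remedy is cheap.

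**What to change.** In Part A SAP section 8.2.6, the matching table, figure and listing footnotes, and Part B SAP section 5.4.2.2 (Overall column), censor patients without the event at the date of the last visit, scheduled or unscheduled, with a recorded disease-status assessment on or before completion or discontinuation.

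For Part A relapse, add that a patient with no assessment after the Week 13 visit is censored at the start of relapse follow-up (Day 1). Without this line the rule is undefined for exactly the patients at issue. Reconcile the origin at the same time: section 8.2.6 counts relapse time from the last PRN1008 dose, while Listing 16.2.4.1.9 counts it from the Week 13 visit.

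Keep the present rule as a sensitivity analysis. If no patient has a gap between last assessment and exit, the two will agree.

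The cost is a sentence or two in each SAP, matching footnotes, one derivation line and the decision on the origin. Disease status by visit is already collected and listed. The change does not address dropout that is itself related to relapse.

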1 INTRODUCTION

The purpose of this document is to describe the final statistical analysis for Part B of the PRN1008-005 study. This statistical analysis plan (SAP) is based on protocol version 7.0 dated 19-Mar-2019 and case report form dated 08-Aug-2018.

The last Part A patient completed the study on 20-Jun-2019. The final Part A study SAP is version 2.0 dated 06-Jan-2019.

2 SYNOPSIS OF STUDY DESIGN & PROCEDURES

2.1 Study Objectives

2.1.1 Primary Objectives

- To evaluate the clinical safety of PRN1008 in patients with PV over a 24-week (Part B) treatment period
- To evaluate the clinical activity of PRN1008 in patients with PV

2.1.2 Secondary Objective

- To evaluate the pharmacokinetics (PK) and the pharmacodynamics (PD) of PRN1008 in patients with PV

2.1.3 Exploratory Objectives

- To evaluate the relationship of PK and PD to each other and to efficacy and safety in this patient population To explore effect of PRN1008 on markers of hemolysis

2.2 Study Design

This is a Phase 2, open-label, pilot cohort study to evaluate the safety, clinical activity, pharmacodynamics, and pharmacodynamics of PRN1008 in patients with newly diagnosed or relapsing PV. An open-label design was chosen for several reasons: PV does not spontaneously remit so there is no placebo effect to account for; clinicians need to know when to use rescue CSs, if necessary, in a timely manner; and lastly, the pilot nature of the investigation itself is best explored in an open-label fashion.

Up to 28 days before enrollment in the study, patients will be required to sign an informed consent form, after which screening assessments will be carried out. Patients must fulfill all entry criteria to be enrolled into the study. Patients who fail to meet the entry criteria may be rescreened at the discretion of the Investigator. Up to 25 male or female patients with newly diagnosed (i.e., naïve to an effective induction treatment regimen) or relapsing, biopsy-proven, mild or moderate PV patients (Pemphigus Disease Activity Index [PDAI] 8 to 45) to enrolled into each parts of the study.

In Part A, the initial dosing was 400 mg twice daily (bid). The duration of study therapy was 12 weeks starting on Day 1 and ending on study Day 84 (total duration of individual subject participation is 28 weeks), with follow-up visits (off-treatment) until Week 29.

In Part B, the initial dosing is 400 mg once daily (qd), with intra-patient dose escalation to 400 mg bid allowed at or after the Week 3 visit for insufficient clinical response (and then again to 600 mg bid if necessary at or after the Week 5 visit). The duration of study therapy is 24 weeks starting on Day 1 and ending on study Day 169, with a follow-up visit (off-treatment) on Day 197 (Week 29). The total duration of individual subject participation is approximately 32 weeks.

Dose Escalation Rules Part B

Current Dose	Inadequate Clinical Response* Dose-Escalation Rules
400 mg qd	Increase to 400 mg bid (allowed at Week 3 visit or later)**
400 mg bid	Increase to 600 mg bid (allowed at Week 5 visit or later)**
600 mg bid	No dose increase possible.

* Investigator discretion: Generally, clinical response is shown by some improvement seen in first 2 weeks with CDA achieved by the Week 5 visit

** Unless tolerability issues preclude dose-escalation

The first dose on Day 1 of Week 1 is supervised in the clinic and the patient observed for approximately 2 hours, at which time a PK/PD sample will be drawn. Day 2 study medication is withheld in the morning in order to gain the trough BTK occupancy approximately 12 (when bid dosing) or approximately 24 hours (when qd dosing) after the prior dose.

Where follow-up is not feasible the next day, another day in the first week of treatment may be used to get through occupancy instead, again withholding dose on the morning of that day to get an occupancy measurement close to 12 (when bid dosing) or approximately 24 (when qd dosing) hours post dose. At other follow-up visits, BTK occupancy can be measured at any time after the usual morning dose of PRN1008.

Part B patients will complete the visit procedures per the Schedule of Assessment (Table 1).

The maximum dose of PRN1008 in both parts of this study, after dose adjustment, will be 600 mg bid.

2.3 Expected Sample Size

Sample size for this pilot study was determined pragmatically by the number of subjects required to determine a preliminary safety profile and a point estimate for the primary endpoint of efficacy. If the clinical response rate is 50%, 25 subjects in each Part will result in an 80% CI of $\pm 13\%$. Results from this pilot study will be used to design confirmatory clinical trials.

